5.2 Variables Used for Stratification of Randomization

There is no randomization for this open-label study.

6.0 Analysis Conventions**Definition of Week 0**

The Week 0 visit date is the date when the first dose of Study M14-347 study drug is received and referred to as Day 1 or Week 0. The Week 0 value for a variable is defined as the last non-missing value on or before the date of the first dose of Study M14-347 study drug.

Definition of Rx Days (Days Relative to the First Dose of Study Drug)

The Rx Day is calculated as the event date minus the date of first dose of study drug plus 1 when the time point of interest is after the date of first dose of study drug, or the event date minus the date of first dose of study drug when the time point of interest is prior to the date of first dose of study drug. It provides a quantitative measure of days between the time point of interest and the first dose date. The day of the first dose of study drug is defined as Rx Day 1, while the day prior to the first study drug dose is defined as Rx Day –1 (there is no Rx Day 0).

Dealing with Multiple Measurements Collected on the Same Day

For efficacy related analyses, if multiple measurements for a particular parameter are collected on the same day for the same subject, the average of those measurements will be used.

For safety related analyses, if multiple measurements are made for a particular laboratory or vital sign parameter on the same day for the same subjects, the later time one will be used if there is time or the average of the values will be used in the analyses of change from Baseline. For summaries and listings for shift from baseline and potentially significant values, all collected values within the pre-specified treatment window will be used.

Definition of Analysis Windows

Since subjects do not always adhere to the study visit schedule, the following rules will be applied to assign actual visits to protocol-specified visits including early termination visits. For each study visit mentioned in the protocol, a nominal or target day will be selected to represent the corresponding visit along with a window around the target day. Windows will be selected in a non-overlapping fashion so that a date collected on the case report form (CRF) does not correspond to multiple visit windows. Moreover, windows will not discard any post-baseline measurement recorded on the CRF. If a subject had 2 or more actual visits in one visit window, the visit closest to the target will be used as

the study visit for that window. If two visits are equidistant from the target day, then the later visit will be used for reporting.

The visit windows and the nominal (target) day for each study visit are shown in the following tables.

Table 3. Visit Windows for Analysis of Efficacy Variables (Except IBDQ, EQ-5D, WPAI, and SES-CD), Laboratory Parameters, and Vital Signs

| Protocol Specified Visit | | | |
|---------------------------------|--------------------|--------------------|--------------------|
| Week | Lower Bound | Nominal Day | Upper Bound |
| 0 | -999 | 1 | 1 |
| 8 | 2 | 57 | 85 |
| 16 | 86 | 113 | 141 |
| 24 | 142 | 169 | 197 |
| 32 | 198 | 225 | 253 |
| 40 | 254 | 281 | 309 |

Table 4. Visit Windows for Analysis of IBDQ, EQ-5D, WPAI, and Abdominal Pain Rating Scale

| Protocol Specified Visit | | | |
|---------------------------------|--------------------|--------------------|--------------------|
| Week | Lower Bound | Nominal Day | Upper Bound |
| 0 | -999 | 1 | 1 |
| 16 | 2 | 113 | 169 |
| 32 | 170 | 225 | 253 |
| 40 | 254 | 281 | 309 |

Table 5. Visit Windows for SES-CD

| Protocol Specified Visit | | | |
|---------------------------------|--------------------|--------------------|--------------------|
| Week | Lower Bound | Nominal Day | Upper Bound |
| 0 | -999 | 1 | 1 |
| 40 | 2 | 281 | 561 |

Note: If an endoscopy was done within 7 days after first dose of Study M14-347, the SES-CD will still be used as Study M14-347 Baseline value.

CD-Related Concomitant Therapy

Subjects in whom systemic corticosteroids that were not being taken at Baseline of Study M14-347 and are initiated during the study or who have dosages of corticosteroids increased to greater than the dose taken at Baseline of Study M14-115 will be censored for efficacy assessments (i.e., will be considered non-responders for categorical endpoints and will have Study M14-115 Baseline values carried forward for non-categorical assessments) from that point through the end of the study. These subjects will continue to be evaluated in the safety population.

The equivalent steroid dose will be determined based on the table below:

| Corticosteroid | Equivalent Dose (mg) |
|--------------------|----------------------|
| Cortisone | 25 |
| Hydrocortisone | 20 |
| Prednisone | 5 |
| Prednisolone | 5 |
| Triamcinolone | 4.0 |
| Methylprednisolone | 4.0 |
| Betamethasone | 0.75 |
| Dexamethasone | 0.75 |
| Budesonide | 1 |
| Beclomethasone | 5 |
| Beclometasone | 5 |

If a subject met the censoring criteria for CD related concomitant therapy during Study M14-115, all binary efficacy endpoints will be No in Study M14-347, all observed values in Study M14-347 will be replaced by Study M14-115 Baseline values.

Dose Escalation

Subjects who had dose escalated to 40 mg ew will be censored for efficacy assessments (i.e., will be considered non-responders for categorical endpoints and will have

Study M14-115 Baseline values carried forward for non-categorical assessments) from that point through the end of the study.

Definition of Missing Data Imputation

Missing data imputation will be done only for efficacy variables (categorical and continuous variables). For the analysis other than efficacy, no imputation will be done for missing values.

Non-Responder Imputation (NRI)

The NRI approach is used for binary efficacy data. These variables can take values of 'Achieved' or 'Not Achieved' or may be missing for any reason including discontinuation from study. According to the NRI imputation approach, all missing values will be considered as 'Not Achieved.'

Observed Case (OC)

Observed case analysis will be performed such that missing values will not be imputed. However, all observed values will be replaced by Study M14-115 Baseline value once subjects met the censoring criteria for CD-related concomitant therapy or dose escalation, whichever is earlier.

Last Observation Carried Forward (LOCF)

For all variables (categorical variables and continuous variables), the following rules will be used for the LOCF approach:

1. Baseline and Pre-Baseline values will not be used to impute the missing Post-Baseline values.
2. Missing values after Study Day 1 will be imputed using the latest non-missing values after Day 1 and prior to the missing value. If there are no non-missing values after Baseline, then the LOCF value will be missing.

Rule for CDAI Calculation

Up to 14 days of diary entries will be evaluated for the CDAI calculation for each visit. The diary entries on the days the subjects receive endoscopy preparation medications, the day of endoscopy procedure, and 2 days after endoscopy procedure will be excluded. For each CDAI subscore, the available scores from the most recent diary days (at least 4 days, up to 7 days) prior to actual day of the study visit will be summed, and then multiplied by the corresponding multiplier to get subtotal score. If available diary entries are fewer than 7 days, the subtotal score will be calculated as (summed total available score/number of days) \times 7 \times corresponding multiplier. The three subtotal scores (number of liquid/very soft stools, abdominal pain rating, and general well-being) will then be rounded to one decimal. The final CDAI is rounded to a whole number.

If a subject has less than 4 days of diary data, the total CDAI score will not be calculated and will be considered missing.

SFPS

SFPS is the CDAI components "Number of liquid or very soft stools" and "Abdominal pain" (Stool [liquid/soft] Frequency + Abdominal Pain Score). The sub-total score for each component is calculated as the sum of the 7 day diary score multiplied by the corresponding multiplier using the same rule for CDAI calculation.

If a subject has less than 4 days of diary data, the SFPS will not be calculated and will be considered missing.

SES-CD Scoring

All colonoscopies shall be performed and recorded in video format. Investigators shall provide their SES-CD assessment on the SES-CD sheet for the baseline and Week 40/Premature Discontinuation visits. The investigator SES-CD are to be entered in the appropriate eCRF, however neither the Investigator's Induction Baseline nor Week 40 SES-CD will be used for the study's efficacy analyses.

Two primary central reviewers will evaluate the videotaped colonoscopies separately and provide their SES-CD to Parexel. A third central reviewer will adjudicate between the two initial reviewers' SES-CD if there is discrepancy in any SES-CD variable. The adjudicator will select the final SES-CD that he/she most agrees with from those provided by the two primary reviewers, and this final SES-CD will be entered into the study database and be used for the study's efficacy analyses. If there is no discrepancy between the two primary central reviewers, that score will be entered into the study database and serve as the SES CD to be used for the study's efficacy analyses.

If there is a missing SES-CD individual variable in the SES-CD that serves as the SES-CD for the study's efficacy analyses, the following imputation rules will be applied:

The missing SES-CD individual variables at Study M14-115 Baseline will be imputed as 0. Study M14-115 Baseline SES-CD will be used to determine endoscopic improvement.

The missing SES-CD individual variables for Study M14-347 Week 0 or Study M14-347 Week 40 will be imputed as 0 if there are 8 or fewer missing individual variables. If more than 8 individual variables are missing, the total SES-CD will be missing for that visit.

Hs-CRP

From November 2014 to December 2015, Roche hs-CRP kit lot 604450 was in use at ICON. In December 2015 ICON altered the study team of a bias in the lot of the Roche Diagnostic C-creative protein high sensitive reagent. ICON then informed the study team of the extent of the under recovery in March 2016. This lot was "retrospectively expired" as the low standard beads agglutinated causing specimen results that are below 5 mg/L to be up to 25% lower than the accurate value. ICON later determined with Roche that the affected samples were those tested from May 18, 2015 to December 2015.

In the Study M14-347 approximately 146 samples were affected according to ICON. AbbVie obtained the final listing of affected samples/results from ICON on August 10, 2016. A correction factor developed by Roche and ICON will be applied to

all affected specimens with a concentration between 0.51 to 4.99 mg/L and will replace the initially provided hs-CRP values in the study database.

For Study M14-347, both Roche and Abbott platform are used to measure hs-CRP. The study team has decided to use Abbott platform for CSR analysis. If hs-CRP was measured by Roche platform only, the value will be converted to Abbott equivalent by a conversion factor.

Definition of Endoscopic Improvement

SES-CD \leq 4 and at least two point reduction from Study M14-115 Baseline and no subscore > 1 in any individual variable.

Definition of CDAI Remission

CDAI $<$ 150

Definition of SFPS Remission

SFPS $<$ 50

Definition of CDAI Response

Decrease in CDAI \geq 70 points from Study M14-115 Baseline

Definition of Enhanced CDAI Response

Decrease in CDAI \geq 100 points from Study M14-115 Baseline

Definition of Endoscopic Response

Decrease in SES-CD $>$ 50% from Study M14-115 Baseline

Definition of IBDQ Response

Increase in IBDQ \geq 16 from Study M14-115 Baseline

Definition of IBDQ Remission

IBDQ \geq 170

Definition of Symptomatic Remission

Average daily stool frequency \leq 1.5 and not worse than Study M14-115 Induction baseline AND average daily abdominal pain \leq 1.0 and not worse than Study M14-115 Induction baseline.

Definition of Symptomatic Response

Average daily stool frequency at least 30% reduction from Study M14-115 Induction baseline and average daily abdominal pain not worse than Study M14-115 Induction baseline OR average daily abdominal pain at least 30% reduction from Study M14-115 Induction baseline and average daily stool frequency not worse than Study M14-115 Induction baseline.

Discontinued Corticosteroid Use at Each Visit Among Subjects Who Used Corticosteroids at Week 0 of Study M14-347

Discontinued steroid use at each visit is based on the steroid use on the date of CDAI measurement for that visit. If the subject has no CDAI for the visit, the steroid use on the nominal day for that visit ([Table 3](#)) will be evaluated.

If a subject discontinued the study, 'discontinued corticosteroid use' will be classified as No from that point through the end of the study.

If a subject met censoring criteria for CD-related concomitant therapy or dose escalation, whichever is earlier, 'discontinued steroid use' will be classified as No from that point through the end of the study.

EuroQol-5D-5L (EQ-5D)

EQ-5D is a standardized measure of health status developed by the EuroQol Group in order to provide a simple, generic measure of health for clinical and economic appraisal.

The EQ-5D consists of 2 pages. The first page measures 5 dimensions of the health status (mobility, self-care, usual activities, pain/discomfort, and anxiety/depression) with 5 levels per dimension (no problems, slight problems, moderate problems, severe problems, and unable corresponding to Level 1 to Level 5 respectively). The second page is an EQ Visual Analogue Scale (EQ VAS). EQ-5D health states, defined by the EQ-5D-5L descriptive system on the first page, may be converted into a single index value. The change from baseline of the index value and EQ VAS will be analyzed and reported. UK scoring algorithm will be used (Table 7).

Table 6. An EQ-5D-5L Value Set for England

| | Central Estimate | Value for Health State 23245 |
|--|------------------|---|
| Mobility | | |
| No Problem | 0 | |
| Slight | 0.051 | 0.051 |
| Moderate | 0.063 | |
| Severe | 0.212 | |
| Unable | 0.275 | |
| Self-Care | | |
| No Problem | 0 | |
| Slight | 0.057 | |
| Moderate | 0.076 | 0.076 |
| Severe | 0.181 | |
| Unable | 0.217 | |
| Usual Activities | | |
| No Problem | 0 | |
| Slight | 0.051 | 0.051 |
| Moderate | 0.067 | |
| Severe | 0.174 | |
| Unable | 0.190 | |
| Pain/Discomfort | | |
| No | 0 | |
| Slight | 0.060 | |
| Moderate | 0.075 | |
| Severe | 0.276 | 0.276 |
| Unable | 0.341 | |
| Anxiety/Depression | | |
| Not | 0 | |
| Slight | 0.079 | |
| Moderate | 0.104 | |
| Severe | 0.296 | |
| Unable | 0.301 | 0.301 |
| The value for health state 23245: 1 – 0.9675 × (sum of the subscores) | | 1 – 0.9675 × (0.051 + 0.076 + 0.051 + 0.276 + 0.301) = 0.270 |

The index value is $1 - 0.9675 \times \text{sum of 5 components based on central estimates.}$

The minimum index value is – 0.281 (health state 55555), and the maximum index value is 1 (health state 11111). (Reference: Devlin N, Shah KK, Feng Y, et al. Valuing health-related quality of life: an EQ-5D-5L value set for England. Health Econ. 2017.).

If one of the 5 dimensions is missing, the EQ-5D index value will be missing.

CD Related Hospitalizations and Major CD Related Events

CD related hospitalizations and major CD related events will be adjudicated according to the hospitalization adjudication charter.

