5.0 Investigational Plan

5.1 Overall Study Design and Plan: Description

This is a Phase 3, multicenter, open-label extension (OLE) study which comprises a 40-week open-label period designed to evaluate the long-term efficacy, safety, and tolerability of adalimumab. Approximately 300 adult subjects who participated and successfully completed Study M14-115 and who meet all of the inclusion criteria and none of the exclusion criteria will be eligible to enroll into this study.

Subjects will be evaluated for entry into Study M14-347 at the final study visit (Week 12) of Study M14-115. A subject's participation in the study is anticipated to be up to 40 weeks. There is a \pm 3-day window for all study visits. An effort will be made to bring the subject back to their original study visit (calculated from Week 0) if they are out of the visit window.

Study visits for clinical and safety assessments will be performed at Weeks 0, 8, 16, 24, 32 and 40/Premature Discontinuation (PD). All subjects will be provided with a paper subject diary in which they will record CD-related symptoms (number of liquid or very soft stools, abdominal pain rating, general well-being) and adalimumab dosing information throughout the study. Blood samples will be collected at various time points for routine labs, along with hs-CRP, adalimumab serum concentrations, anti-adalimumab

antibody (AAA) levels and other biomarker analyses. In addition, stool samples for calprotectin and microbiota will be collected. The stool samples should be taken before starting bowel preparations for endoscopy. Endoscopic evaluation will be performed at Week 40/PD, if the PD occurs after Week 24. CDAI evaluations will be calculated based on entries recorded into the subject's diary at all study visits. The SFPS (Stool [liquid/soft] Frequency + Abdominal Pain Score) will be calculated using the weighted values for the CDAI components "Number of liquid or very soft stools" and "Abdominal pain."

The Week 12 visit of Study M14-115 will be considered Week 0 (Baseline) of Study M14-347. All subjects will receive open-label adalimumab 40 mg every other week (eow) beginning at Week 0. No dose will be administered at Week 40. Subjects may be escalated to adalimumab 40 mg every week (ew) at or after Week 1 should the subject meet the criteria for inadequate response ([Table 1](#)).

Table 1. Inadequate Response

Response Type	Definition

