5.2 Selection of Study Population

5.2.1 Inclusion Criteria

1. Subject must have successfully enrolled in and completed Study M14-115, including the Week 12 ileocolonoscopy.
2. If female, subject is either not of childbearing potential, defined as postmenopausal for at least 1 year or surgically sterile (bilateral tubal ligation, bilateral oophorectomy and/or hysterectomy) or is of childbearing potential and is practicing an approved method of birth control throughout the study and for 150 days after last dose of study drug. Examples of approved methods of birth control which result in a low failure rate (i.e., less than 1% per year) when used consistently are (see local informed consent for more detail):
 - Implants, injectables, some intrauterine devices (IUDs), intrauterine hormone-releasing system (IUS)
 - Sexual abstinence (when in line with preferred and usual lifestyle of the subject)
 - Vasectomized partner
 - Hormonal contraceptives for at least 90 days prior to study drug administration
Note: low-dose progestin-only oral contraceptives such as norethindrone 0.35 mg and lynestrenol 0.5 mg are not considered adequate
3. Subject must be able and willing to give written informed consent and to comply with the requirements of this study protocol.
4. Subject must be able and willing to self-administer SC injections or have a qualified person available to administer SC injections.

Criteria	Rationale
1 – 4	In order to select the appropriate subject population with a disease status representative of the target population for evaluation.

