5.2.2 Exclusion Criteria

1. For any reason subject is considered by the investigator to be an unsuitable candidate.
2. Known hypersensitivity to adalimumab or its excipients.
3. Subject with an active systemic viral infection or any active viral infection that based on the investigator's clinical assessment makes the subject an unsuitable candidate for the study.
4. Positive pregnancy test at Baseline (Week 12 of Study M14-115).
5. Female subject who is considering becoming pregnant during the study.
6. History of malignancy other than a successfully treated non-metastatic cutaneous squamous cell, basal cell carcinoma and/or localized carcinoma in situ of the cervix. If the Week 12 (Study M14-115) colonoscopy shows evidence of dysplasia or a malignancy, subject must not be enrolled in the study.
7. Subject with a poorly controlled medical condition, such as uncontrolled diabetes, unstable ischemic heart disease, moderate or severe congestive heart failure, recent cerebrovascular accidents and any other condition which, in the opinion of the investigator or sponsor, would put the subject at risk by participation in this study.
8. Subject is not in compliance with prior and concomitant medication requirements throughout Study M14-115.
9. History of demyelinating disease (including myelitis) or neurologic symptoms suggestive of demyelinating disease.
10. History of invasive infection (e.g., listeriosis and histoplasmosis) or human immunodeficiency syndrome (HIV).

11. Subject who developed active Tuberculosis (TB) during Study M14-115, or subject who is non-compliant with prophylaxis for latent TB initiated per Study M14-115 procedures.

Criteria	Rationale
1 – 7, 9 – 11	To reduce the risk to subjects or others and/or to exclude underlying conditions that would compromise the subject's safety.
8	To avoid bias for the evaluation of efficacy and safety by concomitant use of other medications or treatments.

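### SAP Table 5: an endoscopy done on Day 2 to 8 is the Week 0 value under the note but also falls in the listed Week 40 window, so applied literally it could count at both ends of the primary endpoint

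*SAP*

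**What the plan says.** SAP Section 6.0 defines the day count and the general baseline rule. On days: "The day of the first dose of study drug is defined as Rx Day 1". On baseline: "The Week 0 value for a variable is defined as the last non-missing value on or before the date of the first dose", meaning the first dose in this extension study.

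Table 5 gives two SES-CD windows: Week 0 from Day -999 to Day 1, and Week 40 from Day 2 to Day 561 with target Day 281. The note under the table makes an exception to the baseline rule: "If an endoscopy was done within 7 days after first dose of Study M14-347, the SES-CD will still be used". The use it names is as the Baseline value for this study.

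The same section sets the principle for all visit windows, in a sentence whose last word is left off here: "Windows will be selected in a non-overlapping fashion so that a date collected on the case report form (CRF) does not correspond to multiple visit". It adds that no post-baseline measurement is to be thrown away, and that when several visits fall in one window the one nearest the target is taken, with ties going to the later visit.

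The primary endpoint (SAP Section 10.2) is improvement at Week 40 among subjects improved at Week 0. NRI is used when the Week 40 SES-CD is missing, with LOCF as the sensitivity analysis. On exit scopes, Protocol Section 5.1 says: "Endoscopic evaluation will be performed at Week 40/PD, if the PD occurs after Week 24".

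**The concern.** The note says what a late entry scope is used for. It does not say that the scope leaves the Week 40 window, and the lower bound of that window was not moved to make room for the exception. A program written from the table and note as they stand can assign the same scope to both visits.

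Where that happens and no later scope exists, one reading decides both whether the subject enters the denominator and whether the subject is a success. NRI should make that subject a failure, but it applies only to a missing Week 40 value, and here the value is present. The primary proportion would then include a subject whose maintenance was never observed. The other SES-CD-only maintenance proportions in SAP Section 10.3 (for example endoscopic response, SES-CD of 2 or less, and SES-CD of 0) use the same windows and have the same gap.

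**Working it through.** The plan has no figure to reproduce: SAP Section 4.3 reports no sample size calculation, and the size of the Week 0 improver group is not stated. The check compares day ranges and then works out the effect per subject.

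**1. Overlap.** Inputs are Table 5, its note, and the rule that the first dose is Day 1.
- Table 5 alone: Week 0 is Day -999 to 1 and Week 40 is Day 2 to 561. Shared days: 0.
- With the note: 1 to 7 days after Day 1 is Day 2 to Day 8. All of these lie in Day 2 to 561. Shared days: 8 - 2 + 1 = 7.
- If the 7 days were instead counted to Rx Day 7, the shared days would be Day 2 to 7, which is 6.

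**2. When the overlap changes a result.** The visit nearest Day 281 is used.
- A Day 8 scope is 281 - 8 = 273 days from the target.
- A later scope on Day 553 is 553 - 281 = 272 days away, so it is nearer. A scope on Day 554 is 273 days away, ties, and wins as the later one.
- So any second scope up to Day 554 displaces a Day 8 entry scope. An earlier entry scope is further from the target and is displaced at least as easily. In practice the overlap matters only when there is no later scope. The obvious route is discontinuation by Week 24, when no exit scope is required; a missed Week 40 scope is another.

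**3. What happens to such a subject.** Take a subject scoped on Day 5 who is improved, has no later scope, and is not censored for escalation or corticosteroids.

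| Reading | Week 0 | Week 40 SES-CD | Primary result |
|---|---|---|---|
| Scope kept at Baseline only | improved (Day 5) | missing | non-responder by NRI |
| Table 5 and note applied literally | improved (Day 5) | Day 5 value | maintained |

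The reference for improvement, the Study M14-115 Baseline, is fixed. The same scope therefore gives the same status at both visits.

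**4. Size.** The denominator D is the same under both readings, because the note fixes Week 0 status either way. With x other successes, the proportion moves from x/D to (x + 1)/D, a change of +1/D per subject. D is not given. Assume D = 50 to 125 of the 252 enrolled (50/252 = 20%, 125/252 = 50%):
- 1/125 = 0.8 percentage points
- 1/50 = 2.0 percentage points

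For k such subjects the change is k/D. The documents do not give k.

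**5. LOCF.** Rule 1 bars Baseline values from filling a missing post-baseline value. Rule 2 fills a missing value with the latest one after Day 1. A Day 5 scope is Baseline by the note and also after Day 1, so rule 1 excludes it and rule 2 admits it. The sensitivity analysis carries the same conflict and cannot be relied on to show the problem.

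**The case against.** The strongest reply is that the SAP already answers the question. Its general principle forbids one date from serving two windows, Table 5 alone respects that principle, and the note is a specific exception that moves the late scope to Baseline. Read together, the date belongs to Week 0 and so not to Week 40. The no-discard sentence does not upset this, since a scope used as Baseline has not been discarded. LOCF rule 1 points the same way, because it shows that Baseline data are not meant to stand in for an outcome.

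Much of this stands. Baseline-only use is the more natural reading, and a reader who inferred that the SAP deliberately plans to compare a scope with itself would go beyond the text. What remains is that nothing in Table 5 or its note puts the principle into effect: the listed bounds still place Day 2 to 8 in Week 40. Two careful programmers could produce different primary results.

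The reply is also right that the affected group is narrow. It needs a Day 2 to 8 entry scope, improvement on it, no later scope, and no censoring. Some early leavers with active disease would already be non-responders through escalation or corticosteroid censoring.

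A reader might also infer that subjects were dosed before entry eligibility was checked, because Protocol Section 5.2.1 requires that "Subject must have successfully enrolled in and completed Study M14-115, including the Week 12 ileocolonoscopy". The documents do not support that as a finding. The note is conditional, no document shows that any such subject exists, and the protocol allows 3 days either side of every visit.

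**Conclusion.** The point holds as an unreconciled conflict inside the SAP. The Table 5 note and the listed Week 40 window share seven days, against the SAP's own windowing principle, and the text leaves open a route by which an early leaver bypasses NRI and counts as maintained.

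Any error is upward only. It is worth 1/D per affected subject, or 0.8 to 2.0 percentage points if D is assumed to be 50 to 125. The number of affected subjects is unknown, probably small and possibly zero. If it is zero, or if the programming keeps the late scope at Baseline only, the primary result does not change. The documents therefore do not show that the primary proportion is inflated. They show that the rule meant to prevent inflation is stated in general terms and not carried into the table that will be programmed.

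**What to change.** Make two edits to SAP Section 6.0.

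- In Table 5, change the lower bound of the Week 40 window from Day 2 to Day 9, counting 7 days after Day 1 as Day 8.
- Add to the note: *A scope used as the Study M14-347 Baseline value is not eligible as the Week 40 value or for LOCF; if no later scope exists, Week 40 SES-CD is missing and NRI applies.*

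This removes all seven shared days and settles the conflict between LOCF rules 1 and 2. The cost is two lines of text and a matching change in the windowing program, with no new data. If any subject is affected, the reported proportion will be slightly lower.
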